8.1. Efficacy Assessments

8.1.1. Primary Efficacy Assessment

Elevated Lp(a) is recognized as an important risk factor for cardiovascular disease. Lp(a) will be collected for each participant at the times shown in the SoA (Section 1.3).

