1.2. Study Design

Study EKBC is a parallel, double-blinded, placebo-controlled, dose-finding, Phase 2 study of LY3473329 in participants with elevated Lp(a) and at high risk for cardiovascular events.

The purpose of this study is to measure difference in percent change in Lp(a) from baseline to 12 weeks with LY3473329 versus placebo in participants with elevated Lp(a) and high risk for cardiovascular events.

Study details include:

- The study duration will be up to 22 weeks.
- The treatment duration will be up to 12 weeks.

All participants will be required to take 4 tablets by mouth every day for 12 weeks to ensure blinding.

Approximately 233 participants will be randomized in a 1:2:2:2 ratio to 1 of the following arms with daily oral dosing for a 12-week treatment period:

- Arm A: 10 mg LY3473329
- Arm B: 60 mg LY3473329
- Arm C: 240 mg LY3473329
- Arm D: placebo

Participants will be stratified by country and baseline Lp(a) (<275 nmol/L, \geq 275 nmol/L as measured by the apo(a) assay defined in Section 4.1).

2. Statistical Hypotheses

The null hypothesis to be tested in relation to the primary estimand is as follows:

• LY3473329 10 mg, 60 mg, and 240 mg are not different from placebo with respect to percent change from baseline in Lp(a)

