4.5.1. Bayesian Analyses for Dose-Response

A Bayesian dose-response analysis will be performed on the percent change from baseline at Week 12 for Lp(a).

The two-component prediction (ITP) model proposed in Fu et al. (2010) and Qu et al. (2019) will be used to estimate Bayesian dose response. The model is as follows:

$$Y_{dit} = f(t; d)(\lambda(d) + s_i) + \epsilon_{it},$$

where Y_{dit} represents the observation for subject *i* at time *t* when taking dose *d*, $\lambda(d)$ is the mean dose response function for dose *d*, s_i is the between-subject random error term, and ϵ_{it} is the within-subject random error term. The mean response function f(t; d) is modeled as

$$f(t;d) = \frac{1-e^{-k(d)t}}{1-e^{-k(d)t}max},$$

where t_{max} is the maximum duration of treatment period and k(d) is the shape parameter for dose d. $s_i \sim N(0, \sigma_s^2)$ and $\epsilon_{it} \sim N(0, \sigma^2)$ are independent, denoting between-subject variation and within-subject variation respectively. Given s_i , $Y_{dit} \sim N(f(t; d)(\lambda(d) + s_i), \sigma^2)$.

A three-parameter logistic regression model may be assumed for the dose response function, $\lambda(d)$. Let α_0 , α_1 , and α_2 represent the basal effect when the dose level is zero (placebo), the maximum effect that can be achieved by any dose level on top of placebo, and the dose level that produces half of the maximum improvement, respectively. Then, the mean function of the parameter of interest is modeled by:

$$\lambda(d) = \alpha_0 + \frac{\alpha_1 d}{\alpha_2 + d}.$$

The estimation of the parameters will be carried out in a Bayesian framework assuming noninformative priors for the hyperparameters in the model as follows:

$$\begin{cases} k(d) \sim \text{Uniform}(0,1), \\ \alpha_0, \alpha_1, \alpha_2 \sim N(0, 100^2), \\ \frac{1}{\sigma^2}, \frac{1}{\sigma_s^2} \sim Gamma(0.01, 0.01). \end{cases}$$

Posterior inference will be drawn for the dose-response of clinical interest, and the 95% credible intervals will also be plotted.

Other dose-response models for $\lambda(d)$ may be explored if the aforementioned dose-response model does not fit the data well, for example, Simple Normal Dynamic Linear Modeling (NDLM) described below.

$$\begin{cases} \lambda(d_1) \sim N(0, \tau) \\ \lambda(d_{i+1}) \sim N(\lambda(d_1), \tau), i = 1, 2 \dots \end{cases}$$

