4.8. Interim Analyses

A planned interim analysis will be conducted when at least 50% enrollment has been completed. The interim analysis will consist of a subset of the primary efficacy estimand analyses specified in the SAP for the primary endpoint, such as the descriptive summaries described in Section 4.1, the MMRM model described in Section 4.1.2.1, and the Bayesian dose-response model described in Section 4.5.1.

Additionally, a planned interim analysis may be conducted when at least 50% of the participants complete Week 12 at Visit 7 or discontinue the study. The details regarding the number of participants and type of analysis will be provided in the assessment committee (AC) charter and in the unblinding plan.

All interims will be for the purpose of internal planning and decision-making and may assess safety, PK, and/or efficacy measures. Additional details related to statistical methods will be described in the SAP. An assessment committee (AC) will be formed to review the interim analyses in an unblinded manner. Only blinded study team members will have contact with the sites. Information that may unblind the study during the analyses will not be reported to study sites or blinded study team members before the study has been unblinded. Study sites will receive information about interim results only if deemed necessary for the safety of the participants. The study will not be stopped based on the efficacy of LY3473329 versus placebo. Therefore, there will be no inflation of the type 1 error rate, and no need to employ an alpha spending function or multiplicity adjustment.

The database lock and primary data analysis for Study EKBC may occur when all participants have completed the study. Unblinded data and results will not be shared with the study sites to maintain blinding at the sites while the study is still ongoing. Details will be specified in the blinding or unblinding plan.

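### SAP 4.5.1 calls k(d) ~ Uniform(0,1) noninformative, but it is a hard limit on speed of onset in an unstated time unit; if t is in weeks and onset is fast, the exploratory dose-response model overstates the Week 12 reduction

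*SAP*

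**What the plan says.** SAP 4.5.1 models each observation as f(t;d)(λ(d) + s_i) plus residual error, where f(t;d) = (1 − e^(−k(d)t)) / (1 − e^(−k(d)·t_max)). Here t_max "is the maximum duration of treatment period and k(d) is the shape parameter for dose d". Since f equals 1 at t_max, λ(d) is the mean response at the end of treatment. The model is fitted "assuming noninformative priors for the hyperparameters in the model as follows", and the list that follows sets k(d) ~ Uniform(0,1).

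No unit is given for t, t_max or k. The rest of the plan counts in weeks. The endpoint is at Week 12, SAP 1.2 states "The treatment duration will be up to 12 weeks", and the Schedule of Activities (Protocol 1.3) places on-treatment Lp(a) at Weeks 1, 2, 4, 8 and 12.

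Other dose-response models for λ(d) "may be explored if the aforementioned dose-response model does not fit the data well". That fallback does not mention f(t;d) or the prior on k(d).

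The analysis is exploratory (SAP 4.5). SAP 4.8 also plans an interim at 50% enrolment, and its examples of what may be run include the MMRM "and the Bayesian dose-response model described in Section 4.5.1".

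**The concern.** A uniform prior with a finite upper end is a constraint on a rate. The α parameters have normal priors with full support and the precisions have unbounded positive support. Only k(d) has a ceiling, and no number of observations can move the posterior past it.

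If Lp(a) falls faster than the ceiling permits, the fitted curve is too low at Weeks 1 and 2. The fit compensates by raising λ(d), the Week 12 effect that the analysis is meant to estimate. Few participants have Week 12 values at an interim triggered by enrolment, so λ(d) is then partly an extrapolation through f and is more exposed.

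The trial is meant to inform the Phase 3 dose (Protocol 4.2), and the SAP rules out dose-to-dose comparisons unless otherwise specified (4.1). The shape of this curve may therefore carry weight in internal decisions. Separately, two programmers could follow the present text with different time units and fit materially different models.

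**Working it through.** **Inputs from the documents.** k(d) ~ Uniform(0,1), t_max = 12 weeks, visits at Weeks 1, 2, 4, 8 and 12. SAP 5 assumes an SD of 20% and a 60% reduction. Its completer counts reproduce: 233 × 2/7 × 0.9 = 59.9 and 233 × 1/7 × 0.9 = 30.0. The documents state no figure for k(d), or for the share of the effect reached at Week 1, that could be checked.

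**Assumptions not in the documents.** t in weeks; true λ = −60; between- and within-subject SDs of 18 and 9 (√(324 + 81) = 20.1, close to the SAP's 20%); 60 participants per dose; a range of onset half-times.

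**1. What the ceiling means.** At k = 1:

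- t in weeks: f(1) = (1 − e^−1)/(1 − e^−12) = 0.632 and f(2) = 0.865. The shortest half-time allowed is ln 2 × 7 = 4.85 days. The prior implied for the Week 1 fraction has median 0.39 and 95% range 0.10 to 0.62.
- t in days: the Week 1 ceiling is 0.999 and the shortest half-time is 0.69 day, so the bound is harmless in practice.
- t in months: the Week 1 ceiling is 0.219.

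**2. Bias with full follow-up.** The model covariance is σ_s² f f′ + σ² I, so for a given k the large-sample estimate of λ is λ_true × (f′f_true)/(f′f), whatever the SDs. When onset is too fast, the best permitted k is 1. Then f = (0.6321, 0.8647, 0.9817, 0.9997, 1) and f′f = 4.1103.

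| True half-time | True k per week | f′f_true | Ratio | Fitted λ (true −60) |
|---|---|---|---|---|
| 2 days | 2.43 | 4.4155 | 1.074 | −64.4 |
| 3 days | 1.62 | 4.3172 | 1.050 | −63.0 |
| 3.5 days | 1.39 | 4.2622 | 1.037 | −62.2 |
| 4 days | 1.21 | 4.2061 | 1.023 | −61.4 |
| 4.5 days | 1.08 | 4.1497 | 1.010 | −60.6 |
| 5 days or more | 0.97 or less | – | 1.000 | −60.0 |

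The SE at the assumed SDs is √((324 + 81/4.1103)/60) = 2.4. It rises to about 2.5 because the misfit inflates the fitted residual SD. Uniform(0,10) per week recovers −60.0 in every row.

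**3. Simulation check.** The full Bayesian model was fitted under both priors to the same simulated data, with SDs of 16 and 12 and 12 data sets per scenario. The Week 12 effects versus placebo for 60 mg and 240 mg were larger reductions under Uniform(0,1) than under Uniform(0,10), by:

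- 2.7 and 2.8 points at a true Week 1 fraction of 75%
- 4.2 and 4.5 points at 85%
- 5.3 and 5.8 points at 95%

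At 55%, below the ceiling, the two priors agreed within 0.3 points. With so few data sets this supports direction and rough size only.

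**4. Interim at 50% enrolment.** Follow-up is staggered, so the expected negative log-likelihood was minimised numerically over λ, k and both SDs. Accrual is assumed uniform.

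| True half-time | 24-week accrual | 36-week accrual | 52-week accrual |
|---|---|---|---|
| 2 days | −69.6 | −67.6 | −66.6 |
| 3 days | −66.5 | −65.2 | −64.5 |
| 3.5 days | −64.7 | −63.8 | −63.3 |

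With 24-week accrual nobody has a Week 12 value yet. With 52 weeks, (26 − 12)/26 = 54% of those enrolled have one.

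For scale, take 30 enrolled per dose and k = 1. The SE is [30 Σ w_m q_m/(81 + 324 q_m)]^(−1/2), where q_m is the sum of f² over the first m visits (0.400, 1.147, 2.111, 3.110, 4.110) and w_m is the share whose last visit is the m-th. With 24-week accrual w = (0.083, 0.167, 0.333, 0.333, 0), the sum is 0.00249 and the SE is 3.7. With 52 weeks w = (0.038, 0.077, 0.154, 0.154, 0.538), the sum is 0.00272 and the SE is 3.5.

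**The case against.** A reader might infer that the prior does bias the Week 12 dose effects. The documents do not support that. Bias needs t in weeks and a half-time below 4.85 days, and neither is stated. Phase 1 is reported only as a decrease over 14 days of dosing, with no time course. Protocol 1.3 says four weeks exceeds five effective half-lives of the drug, which puts that half-life below 28/5 = 5.6 days; but this is a drug half-life, not an onset half-time for Lp(a). Protocol 4.2 expects the nadir by Week 12, and at k = 1 per week the curve is already 98% complete at Week 4 (f(4) = 0.982). That expectation does not point to the harmful case, although it does not exclude it.

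The size is also modest over part of the range: at 4 to 4.5 days the error is well under one SE. The interim figures depend on an accrual pattern that the documents do not give, so only a range can be defended.

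A reader might also infer that the trial's main result is at risk. It is not. The primary comparison is the MMRM of each dose with placebo, which does not use k(d). The interim is for internal planning with no efficacy stopping, the Bayesian model is only one example of what it may contain, and separate dose- or concentration-response modelling is allowed for (SAP 4.4.2).

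All of this stands and limits the point. It does not remove the missing unit, the mislabelled prior, or a fallback clause that leaves the ceiling in place.

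**Conclusion.** The point holds in conditional form and is minor. It is certain that Uniform(0,1) is a hard upper bound on k(d), that its meaning depends on a unit the SAP does not give, and that in weeks it caps Week 1 at 63% and Week 2 at 86% of the Week 12 effect.

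The consequence is conditional on t being in weeks and a true half-time below 4.85 days. For a true −60 the reduction is then overstated, with full follow-up, by about 0.6 points at 4.5 days, 1.4 at 4 days, 3.0 at 3 days and 4.4 at 2 days. At a 50%-enrolment interim, half-times of 3.5 to 2 days give about 3 to 7 points with 52-week accrual and 5 to 10 points with 24-week accrual. These sizes rest on the assumed effect and onset rates and, for the interim figures, also on the assumed SDs and accrual.

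The severity is minor because the model is exploratory or serves internal decisions.

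**What to change.** In SAP 4.5.1:

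- State the unit of t, t_max and k(d).
- Use a prior for k(d) whose support does not bind in that unit. Either keep weeks with, for example, Uniform(0,10) per week (shortest half-time 4.85/10 = 0.49 day), or define t in days and keep Uniform(0,1).
- Stop describing a bounded prior on k(d) as noninformative, or justify the bound.
- Report how λ(d) for the active doses changes under a second, wider prior for k(d), at the final analysis and at any interim that uses the model.

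A rule that withholds λ(d) whenever the posterior of k(d) gathers at its bound would be a poor substitute. It would need a definition of gathering, and it would be ambiguous for placebo: with an effect near zero, k is barely identified there and its posterior follows the prior.

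The cost is a few lines of SAP text, one changed prior in the program and one extra model run per analysis. No change to data collection, sample size or the primary analysis is needed.

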4.6. Safety Analyses

Unless specified otherwise, safety assessments will be guided by an estimand comparing safety of LY3473329 doses with placebo irrespective of adherence to intervention or initiation of Lp(a) modifying medications. Thus, safety analyses will be conducted using the SS (Section 3).

4.6.1. Extent of Exposure

Duration of exposure to study intervention will be summarized by treatment group. Exposure will be summarized and calculated for the treatment period being considered as the date of last dose of study intervention minus the date of first dose of study intervention plus 1 day using safety participants. Duration on study (date of end of study participation – date of randomization + 1) will also be summarized by treatment group.

Descriptive statistics (including n, mean, SD, minimum, first quartile, median, third quartile, and maximum) will be provided.

4.6.2. Adverse Events

A treatment-emergent adverse event (TEAE) is defined as an event that first occurred or worsened in severity after first dose. The Medical Dictionary for Regulatory Activities (MedDRA) Lowest Level Term (LLT) will be used in the treatment-emergent derivation. The maximum severity for each LLT during the baseline period including ongoing medical history will be used as baseline severity. Events with a missing baseline severity will be treated as "mild" in severity for determining treatment-emergence. Events with a missing severity during the postbaseline period will be treated as "severe" and treatment-emergence will be determined by comparing to baseline severity.

For events occurring on the day of first taking study medication, the case report form collected information (for example, treatment emergent flag, start time of study treatment and event) will be used to determine whether the event was pre- versus post-treatment if available. If the relevant information is not available, then the events will be counted as posttreatment.

The counts and percentages of participants with TEAEs will be summarized by treatment using MedDRA Preferred Term (PT) nested within System Organ Class (SOC). Statistical comparisons will be applied at both the SOC and PT levels. Events will be ordered by decreasing frequency within SOC. The SOC will be in alphabetical order. For events that are sex-specific, the denominator and computation of the percentage will include only participants from the given sex.

An overview of the number and percentage of participants who experienced a TEAE, serious adverse event, death, discontinued from study treatment or study due to an AE, and relationship to study drug will be summarized by treatment.

The counts and percentages of patients with TEAEs by maximum severity will be summarized by treatment using MedDRA PT. For each participant and TEAE, the maximum severity for the MedDRA PT is the maximum postbaseline severity observed from all associated LLTs mapping to the MedDRA PT. The maximum severity will be determined based on the non-missing severities. If all severities are missing for the defined postbaseline period of interest, it will show as missing in the table.

4.6.3. Patient Narratives

Patient narratives will be provided for all participants who experience any of the following "notable" events:

- death
- serious adverse event, or
- permanent discontinuation of study treatment due to AEs.

Patient narratives (patient level data and summary paragraph) will be provided for participants in the randomized population with at least 1 notable event.

4.6.4. Vital Signs

If multiple records of an individual's vital signs are collected at the same visit, they will be averaged prior to being used for data summaries and analyses.

Descriptive summaries by treatment and by nominal visit will be provided for baseline and postbaseline values, as well as change from baseline values.

Treatment differences in mean change will be analyzed using the MMRM model as described in Section 4.1.2.1.

Counts and percentages of participants with treatment-emergent abnormal sitting systolic blood pressure (BP), sitting diastolic BP, and pulse rate will be presented by treatment group. Both planned and unplanned measurements will be included in the analysis. The criteria for identifying patients with treatment-emergent vital sign abnormalities are stated in Table EKBC.4.4.

Parameter	Low	High
Systolic BP (mm Hg)	≤90 and decrease from	≥129 and increase from
(sitting)	baseline ≥20	baseline ≥20
Diastolic BP (mm Hg)	\leq 50 and decrease from	\geq 90 and increase from
(sitting)	baseline ≥10	baseline ≥10
Pulse (bpm)	<50 and decrease from	>100 and increase from
(sitting)	baseline ≥15	baseline ≥15

Table EKBC.4.4. Categorical Criteria for Abnormal Treatment-Emergent Blood Pressure and Pulse Measurements

Abbreviations: BP = blood pressure; bpm = beats per minute.

Counts and percentages of participants with maximum systolic BP and diastolic BP will be summarized by treatment groups for the following categories using safety participants.

Systolic Blood Pressure (mm Hg)	Diastolic Blood Pressure (mm Hg)
<90	<60
≥90	>60
≥120	>90
≥140	>110
≥160	≥120
≥180	

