5.2. Exclusion Criteria

Participants are excluded from the study if any of the following criteria apply:

Medical Conditions

9. Have a history or presence of an underlying disease, or surgical, physical, medical, or psychiatric condition that, in the opinion of the investigator, would potentially affect participant safety within the study or interfere with participating in or completing the study or with the interpretation of data.

10. Any of the following, or other events indicating unstable medical condition in the opinion of the investigator, within 3 months of Visit 1:

- a. major surgery
- b. coronary, carotid, or peripheral arterial revascularization
- c. stroke or transient ischemic attack
- d. myocardial infarction or unstable angina
- e. acute limb ischemia.
- 11. Have, in the 6 months prior to Visit 1, uncontrolled Type 1 or Type 2 diabetes, defined as an episode of ketoacidosis or hyperosmolar state requiring hospitalization, or have a hemoglobin A1c (HbA1c) ≥8% at Visit 1.
- 12. Have uncontrolled hypertension with a resting blood pressure ≥160 mm Hg systolic and/or ≥100 mm Hg diastolic at Visit 1; a repeat measure is allowed.
- 13. New York Health Association Class III or IV heart failure or last known left ventricular ejection fraction <30%.
- 14. Active or acute infection requiring systemic antiviral or antimicrobial therapy that will not be completed prior to Visit 2.
- 15. Malignancy within 5 years, except for basal or squamous cell carcinoma of the skin or carcinoma in situ of the cervix that has been successfully treated.
- 16. Recent history of, or current drug or alcohol abuse in the opinion of the investigator.
- 17. Have 2 or more clinically significant or severe drug allergies, or severe post-treatment hypersensitivity reactions, including, but not limited to
 - a. erythema multiforme major
 - b. linear immunoglobulin A dermatosis
 - c. toxic epidermal necrolysis
 - d. exfoliative dermatitis.
- 18. Hypersensitivity to the active substance or to any of the excipients.
- 19. Have a current infection with hepatitis B virus (HBV), that is, positive for hepatitis B surface antigen (HBsAg) and/or PCR positive for HBV deoxyribonucleic acid (DNA) (Section 8.2.5).
- 20. Have a current infection with hepatitis C virus (HCV), that is, positive for HCV ribonucleic acid (RNA) (Section 8.2.6).
- 21. Have human immunodeficiency virus (HIV) infection.

Prior/Concomitant therapy

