9.3.5.1. Laboratory Measures, Vital Signs, and Electrocardiograms

Laboratory measures and vital signs will be summarized for each scheduled visit by

- actual measures at baseline and postbaseline
- change from baseline to postbaseline, or
- percent change from baseline to postbaseline.

The laboratory measures may be log transformed before statistical analyses, if deemed necessary. Continuous variables, as well as the change from baseline for these variables or other appropriate transformed variables, will be analyzed by MMRM models as described in Section 9.3.1.

The percentages of participants with treatment-emergent abnormal, high, or low measures, including laboratory and vital parameters, will be summarized and compared between treatment groups using Fisher's exact test.

The analysis details will be provided in the SAP.

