4.1.1. Definition of Baseline

Unless specified otherwise, baseline is defined as the last non-missing measurement recorded on or before the randomization visit (Visit 2), prior to the first dose of intervention, which in most cases will be the measurement recorded at Week 0 (Visit 2). For the safety related parameters, the definition of baseline and postbaseline are specified in Table EKBC.4.2.

Study Period/	Particinant Population	Baseline Observations	Postbaseline Observations
Analysis Type	i articipant i opulation	Daschile Observations	i ostbasenne observations
1.1) Treatment-	All randomized participants	The baseline period is	Starts at or after the first
Emergent Adverse	who are exposed to at least	defined as the start of	dose of study drug and ends
Events (SS)	1 dose of study drug	screening and ends prior to	at the conclusion of the
		the first dose of study drug.	study period.
1.2) Treatment-	All randomized participants	Baseline will be all	Postbaseline will be defined
Emergent Abnormal	who are exposed to at least	scheduled and unscheduled	as above (1.1). All
Labs and Vital Signs	1 dose of study drug who	measurements recorded	scheduled and unscheduled
(SS)	have a normal baseline	during the baseline period as	measurements will be
	(with respect to the direction	defined above (1.1).	included.
	being analyzed) and a post-		
	baseline observation		
1.3) Change from	All randomized participants	The last scheduled non-	Postbaseline will be defined
Last Baseline to each	who are exposed to at least	missing assessment	as above (1.1). Only
postbaseline week	1 dose of study drug and	recorded prior to the first	scheduled visits will be
and to last	have a baseline and at least	dose of study treatment	included. The early
postbaseline for Labs,	1 post-baseline observation	during the baseline period	discontinuation visits are
Vital Signs (SS)		defined above (1.1).	considered scheduled visits.

 Table EKBC.4.2.
 Baseline and Postbaseline Definitions for Safety Analyses

Abbreviations: ED = early discontinuation; SS = safety set.

Note: for the continuous analysis of clinical laboratory tests, unscheduled measurements are excluded from analysis to reduce bias. The early discontinuation visits are considered scheduled visits.

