4.1.2.3. Analysis method for safety

Unless specified otherwise, safety assessments will be guided by an estimand comparing safety of LY3473329 doses with placebo irrespective of adherence to intervention or initiation of Lp(a) modifying medications. Thus, safety analyses will be conducted using the SS (Section 3).

While considering treatment-emergent abnormal safety laboratory values and vital signs, the baseline observation period starts from the screening visit and ends prior to the first dose of study

intervention, wherein all scheduled and unscheduled measurements will be included. Baseline for the corresponding safety analysis will be the maximum/minimum (i.e., the most extreme/abnormal) from all these measurements during the baseline period. For postbaseline measurements, all scheduled and unscheduled measurements in the analysis period will be included. Table EKBC.4.2 the definition of baseline, postbaseline, and patient population for different safety endpoints.

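### An undefined normal-baseline condition can drop participants with raised pre-dose blood pressure from the one table that counts threshold-plus-change rises by arm

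*SAP*

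**What the plan says.** Four provisions bear on this point.

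- **The event** (SAP 4.6.4, Table EKBC.4.4). High systolic is "≥129 and increase from" baseline of at least 20 mm Hg. High diastolic is 90 or more with a rise of at least 10.
- **Who is counted** (SAP 4.1.1, Table EKBC.4.2, row 1.2, which covers laboratory tests and vital signs together). Treated participants must "have a normal baseline", judged "with respect to the direction" under analysis, and have a post-baseline observation.
- **What baseline is** (SAP 4.1.2.3). "Baseline for the corresponding safety analysis will be the maximum/minimum (i.e., the most extreme/abnormal) from all these measurements during the baseline period". That period runs from screening to the first dose and includes unscheduled readings. SAP 4.6.4 adds that repeat vital-sign records at one visit are averaged first.
- **Who may enter** (Protocol 5.2, criterion 12). Exclusion is for "uncontrolled hypertension with a resting blood pressure ≥160 mm Hg systolic and/or ≥100 mm Hg diastolic at Visit 1; a repeat measure is allowed". Visit 1 values up to 159 systolic and 99 diastolic are therefore eligible.

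Protocol 9.3.5.1 plans to compare between groups "The percentages of participants with treatment-emergent abnormal, high, or low measures, including laboratory and vital parameters". It states no normal-baseline condition and leaves the details to the SAP. SAP 4.6.4 does not repeat the condition either.

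**The concern.** A normal-baseline condition does useful work for a laboratory analyte judged only against a limit: it stops a value that was already abnormal from being called emergent. Table EKBC.4.4 does not need it. Its change requirement, measured from the highest pre-dose value, already establishes emergence and guards against a chance high reading. Adding the condition only removes participants.

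The SAP also does not say what a normal vital sign is. The low and high limits in SAP 4.6.6 come from the performing laboratory and cover laboratory tests only. Two programmers could produce different denominators from the same text.

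At stake is coverage of a safety table in a population chosen for high cardiovascular risk. Participants who start with raised pressure are those in whom a further rise of 20 mm Hg or more would be of most interest.

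**Working it through.** **Step 1: two readings of normal.**
- *Reading A.* Normal means below the level in Table EKBC.4.4, the only vital-sign limit tied to this analysis: below 129 systolic, below 90 diastolic.
- *Reading B.* Abnormal means meeting the whole Table EKBC.4.4 rule. A baseline value cannot show a change from itself, so nobody is abnormal at baseline and the condition removes no one.

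Reading A is the natural one, because under B the condition would have no effect. It remains an inference.

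**Step 2: consequence of Reading A.**

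| Highest pre-dose value | Highest post-dose value | Rise | Meets level and change? | Counted? |
|---|---|---|---|---|
| 109 systolic | 129 | 20 | yes | yes |
| 135 systolic | 185 | 50 | yes | no, baseline at or above 129 |
| 95 diastolic | 120 | 25 | yes | no, baseline at or above 90 |

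All three starting values are eligible under criterion 12.

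**Step 3: share removed.** The documents give no figure to reproduce and no baseline blood pressure distribution, so the inputs are assumptions:
- one visit value at Visit 1 and one at Visit 2 (the Schedule of Activities has vital signs at both);
- bivariate normal, mean 120-140, SD 13-16, correlation 0.6;
- Visit 1 below 160.

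Share removed = P(max(Visit 1, Visit 2) ≥ 129, given Visit 1 < 160), by simulation:

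| Mean systolic | Share removed (SD 13-16) |
|---|---|
| 120 | 36-41% |
| 125 | 52-54% |
| 130 | 66-68% |
| 135 | 77-80% |
| 140 | 85-90% |

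On a wider grid (SD 12-18, correlation 0.5-0.8), the range is about 30% to 92%. The share passes 50% at a mean of 122-126. On that grid, using the larger of two visit values instead of one adds about 7 to 17 percentage points.

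**Step 4: participants.** Randomization is 233 in a 1:2:2:2 ratio: 233/7 ≈ 33 in the 10 mg arm and 2 × 233/7 ≈ 67 in each other arm.
- At 36% removed: 0.36 × 233 ≈ 84 out, leaving 0.64 × 33 ≈ 21 and 0.64 × 67 ≈ 43 per arm.
- At 90% removed: 0.90 × 233 ≈ 210 out, leaving 0.10 × 33 ≈ 3 and 0.10 × 67 ≈ 7 per arm.

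**Step 5: events.** Take six post-baseline visit values (Visits 3 to 7 and 801) and no true shift, on the wider grid. Of all participants meeting the level-plus-change rule, those removed by the condition make up about 8-27% at mean 120, 34-45% at mean 130 and 64-72% at mean 140. The share of events lost is smaller than the share of participants lost, but not negligible.

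**The case against.** The strongest reply is that the data are not lost. SAP 4.6.4 also reports maximum systolic and diastolic categories by arm for all safety participants, so the 135-to-185 participant appears at 180 or more. The same values enter the by-visit change summaries and the mean-change MMRM. Protocol 10.3.1 makes a clinically significant worsening of vital signs an adverse event, and SAP 4.6.2 counts those by arm. This stands: a reader might infer that large rises go uncounted, and the documents do not support that. What remains is that maximum categories ignore the starting value (158 to 162 and 120 to 162 look alike), a mean does not count individuals, and adverse event reporting depends on investigator judgement.

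Second, the restriction uses pre-dose values only and applies equally in every arm. This also stands: it narrows the population described but does not bias the comparison.

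Third, same-visit readings are averaged, so one high reading among repeats need not set the baseline. This is correct, and is why the check uses visit values.

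Fourth, 129 matches none of the bands in the same section (120, 140, 160, 180). A reader might take it for an error, but the two displays serve different purposes and need not share limits. Nor does the problem depend on 129: for means of 125-135, a limit of 140 would still remove 19% to 49%.

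**Conclusion.** The point holds as a limited defect in one safety table. SAP Table EKBC.4.2 row 1.2 imposes a normal-baseline condition on vital signs without defining normal, on top of an event rule that already has its own change requirement. On the natural reading, eligible participants with a highest pre-dose visit value of 129-159 systolic or 90-99 diastolic cannot be counted as high, however far they rise.

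The size rests on assumption: about 36% to 90% of participants for mean systolic 120-140, SD 13-16 and correlation 0.6, and none under Reading B. A reader might conclude that most of the population is removed. The documents do not establish that, because it requires a mean above roughly 122-126 and no baseline figure is given. A substantial share is the supportable description.

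The primary analysis is unaffected, no bias between arms arises, and the protocol's silence on the condition is not a contradiction because it defers detail to the SAP. The point is worth acting on because this is the only planned table that counts threshold-plus-change rises by arm, and the correction is cheap.

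**What to change.** In SAP Table EKBC.4.2 row 1.2, limit the normal-baseline condition to laboratory analytes. For vital signs, state that the population is all safety-set participants with a baseline and at least one post-baseline value. Let Table EKBC.4.4 define the event: level plus change, measured from the most extreme pre-dose value as in Section 4.1.2.3. Apply this to systolic, diastolic and pulse in both directions.

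If the sponsor prefers to keep the condition, the SAP should at least define normal for each vital sign and report the number removed per arm.

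The cost is SAP wording and programming, settled before unblinding, with no new data. Reported event counts will be higher than under the current rule, and the table will depart from the normal-baseline convention used for laboratory tests, which a footnote can explain.
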